## 2. OBJECTIVES

**Primary:** To evaluate the number of days patients spend with a grade 3 or higher toxicity (among those considered). The specific toxicities that are the object of evaluation are chosen among those that are clinically relevant and are more likely responsible for a reduction of treatment adherence and, then, a reduction of the benefit from such treatment.

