**3.2 Patients'classification and randomisation**

Eligible patients are split up into three subgroups according to the oncological treatment

- Patients on adjuvant chemotherapy
- Patients treated with oral targeted therapy for the first time
- Patients treated with immunotherapy for the first time

Within each subgroup patients are randomised to receive:

- ✗ a periodical nurse monitoring phone call, that is planned and agreed with the patient, together with an information sheet with advice about prevention and treatment of toxicities (Experimental group)
- ✗ an information sheet with advice about prevention and treatment of toxicities (Standard group).

1:1 randomisation will be performed via computer using the randomly permuted blocks system.

All participants are to give their written informed consent.

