### **3.3 Study duration**

The study will last 24 months. Patients' accrual will have a duration of 18 months, from the beginning of the trial. The study period will be 4 months for the immunotherapy and targeted therapy groups and 6 months for the adjuvant chemotherapy group.

The study can be interrupted earlier in case of oncological treatment discontinuation because of disease progression, unacceptable toxicity, or withdrawal of consent by the patient, or patient's death. In case of temporary suspension of the oncological treatment, patients will continue to be monitored according to the group they are assigned. The study ends with the end of the monitoring period, that is with the last phone call to the last enrolled patient.

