#### Group A

Considering the lack of data from the literature about the duration of side effects, especially grade 3 and 4, but estimating a prevalence of about 15%, considering a power of 0.9 and an alpha value of 0.05, it is then necessary to have 207 patients for each arm of the study to show a reduction from 15% to 5% of the proportion of days spent with a grade 3 or higher toxicity.

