#### Groups B and C

Considering the same lack of data, but estimating a prevalence of about 25%, considering a power of 0.72 and an alpha value of 0.05, it is then necessary to have 50 patients per

arm per group to show a reduction from 25% to 5% of the proportion of days spent with a grade 3 or higher toxicity.

The entire sample size is then formed by 614 patients, to be found among the 63 involved centres.

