## **5.3 Data analysis**

Qualitative variables are synthesized in absolute frequencies and percentages; quantitative ones through mean and standard deviation, maximum and minimum, median and interquartile range. The evaluation of the statistical significance of the differences between two main groups (nurse monitoring vs standard monitoring) will be analyzed through the Student's t-test for dependent groups in case of quantitative parameters. The chi-square test will be used to evaluate the statistical significance of the differences in qualitative parameters. The comparisons among groups will be performed at the end of the study. The statistical significance of the variations in time of quantitative variables will be performed through the two-way analysis of variance (ANOVA). A secondary analysis will be performed, aiming at evaluating the statistical significance of the differences in all the other parameters between the two groups.

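### Section 5.3 assigns a paired t-test to the comparison of nurse and standard monitoring, but the two arms are separate, individually randomised patients with no pairing.

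*Protocol*

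**What the plan says.** Protocol section 5.3 names the contrast as nurse monitoring against standard monitoring and assigns to it a Student's "t-test for dependent groups in case of quantitative parameters". Qualitative outcomes get a chi-square test. Change over time is handled separately: "variations in time of quantitative variables will be performed through the two-way analysis of variance".

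Section 3.2 sets the design: "Within each subgroup patients are randomised to receive" one arm or the other, and "1:1 randomisation will be performed via computer using the randomly permuted blocks system". Section 3 describes two parallel arms, the information sheet with or without nurse calls.

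The primary objective in section 2 is a quantity: "To evaluate the number of days patients spend with a grade 3 or higher toxicity". Section 5.3 does not say which test applies to it.

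Section 5.1 sizes Group A ("it is then necessary to have 207 patients for each arm of the study", power 0.9, alpha 0.05, 15% to 5%) and Groups B and C (50 per arm per group, "considering a power of 0.72 and an alpha value of 0.05", 25% to 5%), 614 patients in all. It states no within-pair correlation.

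**The concern.** A dependent-groups t-test analyses differences within pairs. Here no pairs exist. Permuted blocks balance the numbers in the two arms; they do not link a given nurse-arm patient to a given control.

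The sentence cannot be read as a before-and-after comparison within patients, because it names the between-arm contrast and change over time has its own method. It is also the only between-arm test that the protocol names for quantitative outcomes. On the natural reading it therefore covers the primary outcome (days with grade 3 or higher toxicity), as well as hospital days and visit counts.

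Two things follow if the text is applied literally:

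- If the arms differ in analysable size, the surplus patients in the larger arm cannot enter the test.
- If the arms are equal, the analyst must choose a pairing, and the p-value depends on that choice. If the choice is made after the data are seen, a borderline result can be moved to either side of 0.05.

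**Working it through.** **1. The protocol's own sample size.** Inputs are from section 5.1, with alpha taken as two-sided (the protocol does not state sidedness). For two independent proportions with pooled variance, where p̄ is the mean of p1 and p2 and d = p1 − p2:

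n = [z(1−α/2)·√(2p̄(1−p̄)) + z(power)·√(p1(1−p1) + p2(1−p2))]² / d²

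Continuity-corrected: n' = (n/4)·[1 + √(1 + 4/(n·d))]²

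- Group A, 0.15 vs 0.05, power 0.90: n = (0.8315 + 0.5361)² / 0.01 = 187.0, and n' = 206.6, so 207 per arm.
- Groups B and C, 0.25 vs 0.05, power 0.72: n = (0.9897 + 0.2825)² / 0.04 = 40.5, and n' = 49.97, so 50 per arm.
- Total: 2×207 + 4×50 = 614.

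All three stated figures reproduce. The trial was sized as two independent groups.

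**2. What an arbitrary pairing does.** With equal arms of size n and similar variances, the mean difference is the same in both tests. The variance of the difference changes by the factor 1 − r, where r is the correlation that the pairing happens to produce:

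t(paired) ≈ t(independent) / √(1 − r)

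For unrelated patients r averages zero, with standard deviation about 1/√(n−1). Degrees of freedom fall from 98 to 49 at 50 per arm and from 412 to 206 at 207 per arm. The critical values move from 1.984 to 2.010 and from 1.966 to 1.972.

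Take data whose independent-test p is exactly 0.05:

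| n per arm | SD of r | 95% limits of r | t(paired) range | p on n−1 df |
|---|---|---|---|---|
| 50 | 0.143 | ±0.280 | 1.984/√1.280 = 1.754 to 1.984/√0.720 = 2.339 | 0.086 to 0.023 |
| 207 | 0.070 | ±0.137 | 1.966/√1.137 = 1.844 to 1.966/√0.863 = 2.115 | 0.067 to 0.036 |

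Simulation agrees (200 normal data sets shifted to an independent p of 0.05, 1,000 pairings each): 0.024 to 0.085 at 50 per arm and 0.036 to 0.067 at 207 per arm.

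**3. Long-run behaviour.** 40,000 simulated trials per setting, normal data with SD 1, one random pairing per trial. Effects are 0, or the size giving the independent test power of 0.72 (0.514 SD, n = 50) or 0.90 (0.319 SD, n = 207).

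| n per arm | Effect | Paired rejects | Independent rejects | Verdict differs |
|---|---|---|---|---|
| 50 | none | 0.050 | 0.051 | 1.3% |
| 50 | 0.514 SD | 0.713 | 0.722 | 4.1% |
| 207 | none | 0.049 | 0.049 | 0.6% |
| 207 | 0.319 SD | 0.903 | 0.904 | 1.0% |

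Repeat runs gave 3.8% to 3.9% for the second row; the others moved by about 0.1 percentage points at most.

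**4. Non-normal data.** The protocol gives no distribution for toxicity days, so this step is an assumption: 25% to 75% zeros in one arm, 40% fewer non-zero patients in the other, and exponential durations with mean 20 days. At 50 per arm, with an independent p between 0.045 and 0.055, the 95% range of paired p is 0.021 to 0.078 with 25% zeros and 0.026 to 0.063 with 75% zeros. The conclusion does not depend on normality.

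**The case against.** **A slip of wording.** The protocol has others (its index prints casualty for causality), and an analyst facing two unpaired arms would probably run an independent test anyway. That is plausible, but it cannot be shown, no other sentence corrects it, and the text as it stands prescribes the wrong test. The statistical analysis plan, which is not at hand, may name the right one. It would then contradict the protocol until section 5.3 is amended.

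**Little numerical harm.** This stands. Type I error is preserved, power falls by at most 0.9 percentage points, and the wide p-value ranges apply to borderline results only. All these figures also model random pairing, which the protocol never specifies.

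**The primary outcome may not be covered.** Section 5.1 sizes the trial on proportions, which would go with the chi-square test. The objective in section 2 is a number of days, so the t-test is the more natural reading, but it remains an inference.

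**Early stopping does not make the arms unequal.** Section 3.3 says "The study can be interrupted earlier in case of oncological treatment discontinuation", but a patient who stops early has contributed days and need not leave the analysis. This is right: early stopping shortens follow-up and does not by itself change the number analysed. Unequal arms can still arise from an incomplete last block or from patients without data. The main point does not need them, because no pairing is defined even when the arms are equal.

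**Conclusion.** The concern holds. Section 5.3 prescribes a paired test for a contrast between unpaired, individually randomised arms, which contradicts section 3.2 and the independent-groups sizing in section 5.1. It should be corrected because the analysis is undefined as written, not because of a quantified loss. Averaged over trials the effect is small: the verdict differs in 0.6% to 4.1% of them. It becomes material near the threshold, where p can move between about 0.02 and 0.09 at 50 per arm through the choice of pairing alone. These sizes assume equal arms, random pairing and, for the main figures, normal data. That the test is undefined rests on none of these assumptions. That it reaches the primary outcome is the natural reading of sections 2 and 5.3, not an explicit statement.

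**What to change.** In section 5.3, replace dependent with independent in the sentence on the t-test. The version that allows unequal variances is one suitable choice. If Groups A, B and C are to be pooled, a linear model with arm as factor and treatment subgroup as stratum would also fit the design; this is optional. If a statistical analysis plan exists, check that it names the same test.

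The cost is one word in a protocol amendment. No new data or patients are needed. The figures of 207 and 50 per arm and 614 in total stay, because they already come from an independent-groups calculation.

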**Secondary:**

- ✓ Incidence and duration of grade 1-2 toxicities;
- ✓ Number of emergency room accesses and unplanned specialist visits;
- ✓ Number of hospital admissions and days spent in the hospital because of treatment -related toxicities
- ✓ Evaluation of quality of life.

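### Section 5.3 compares visits, admissions and hospital days without allowing for time observed, so early exit that differs by arm would bias these secondary comparisons

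*Protocol*

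**What the plan says.** Section 2 of the protocol lists among its secondary objectives "Number of emergency room accesses and unplanned specialist visits" and "Number of hospital admissions and days spent in the hospital because of treatment -related toxicities". Section 4 again speaks of monitoring the number of these events in both arms. Neither place gives a denominator or a rate.

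For analysis, section 5.3 prescribes a Student's "t-test for dependent groups in case of quantitative parameters", a chi-square test for qualitative outcomes and a two-way ANOVA for variation over time. It adds a secondary analysis "evaluating the statistical significance of the differences in all the other parameters between the two groups". It mentions no count model, person-time or offset. (Naming a dependent-groups test for two independently randomised arms is a separate error. Correcting it would leave the present point untouched.)

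On follow-up, section 3.3 states: "The study period will be 4 months for the immunotherapy and targeted therapy groups and 6 months for the adjuvant chemotherapy group". It then adds: "The study can be interrupted earlier in case of oncological treatment discontinuation because of disease progression, unacceptable toxicity, or withdrawal of consent", and also names death. Patients whose treatment is only temporarily suspended stay under monitoring.

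The primary outcome is treated differently: section 5.1 expresses it as a proportion of days, which scales for time observed. Nothing similar is stated for the resource-use counts.

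**The concern.** A patient observed for three months has less opportunity to visit an emergency room than one observed for six. If the two arms are observed for different lengths of time, a difference in mean counts mixes the event rate with the time at risk.

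One reason for ending observation, unacceptable toxicity, is something the intervention is meant to influence. Section 1 suggests that better toxicity management may help patients receive their planned treatment and may limit inadequate withdrawals. If that happens, experimental patients are observed longer and accrue more events at the same rate. The bias then runs against the nurse calls, on the endpoints that describe their effect on health-service use.

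**Working it through.** **The plan's own figures.** The protocol gives no event rate, dispersion, share of zeros, dropout or power for these endpoints, so there is nothing to reproduce for them. The primary sample sizes do reproduce, with a two-sided continuity-corrected comparison of two proportions: 207 per arm (15% to 5%, power 0.90) and 50 per arm (25% to 5%, power 0.72). The total is 2 × 207 + 4 × 50 = 614. I use 207 and 50 below.

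**Planned duration.** Section 3.2 states "Within each subgroup patients are randomised to receive", so the 4-month and 6-month windows are balanced between arms. Only early exit that differs by arm can bias the comparison.

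**Assumptions (mine, not the protocol's).** Counts are gamma-Poisson with shape 0.5 and control mean 1 per full window. Exit is exponential with hazard λ per window, independent of the event rate, and truncated at the window. With T the fraction of the window observed and r the rate per window:
- E[T] = (1 − e^−λ)/λ and E[T²] = 2[1 − e^−λ(1 + λ)]/λ²
- mean count m = rE[T]; variance v = m + 3r²E[T²] − m²
- t-test on counts: z = (m_C − m_E)/√[(v_C + v_E)/n]
- rate comparison: variance of the log rate per arm = (m + 2r²E[T²])/(n m²)
- rejection probability = Φ(|z| − 1.96) + Φ(−|z| − 1.96)

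**Moderate imbalance.** Control λ = 0.5 gives E[T] = 0.787 and E[T²] = 0.722. Experimental λ = 0.3 gives 0.864 and 0.821. At equal rates the ratio of mean counts is 0.864/0.787 = 1.10.
- *50 per arm, rate ratio 0.5.* Means 0.787 and 0.432; variances 2.333 and 0.861. z = 0.355/√(3.194/50) = 0.355/0.253 = 1.405, power 0.29. Rate comparison: SE = √[(3.601 + 4.514)/50] = 0.403, z = 0.693/0.403 = 1.72, power 0.41.
- *207 per arm, rate ratio 0.6.* Means 0.787 and 0.518; variances 2.333 and 1.136. z = 0.269/0.129 = 2.075, power 0.55. Rate comparison: SE = √[(3.601 + 4.129)/207] = 0.193, z = 0.511/0.193 = 2.64, power 0.75.
- *No true effect.* Means differ by 0.077. At 50 per arm z = 0.077/0.313 = 0.25, rejection 5.7%. At 207 per arm z = 0.077/0.154 = 0.50, rejection 7.9%.

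**Extreme bound.** λ = 0.8 versus 0.2 gives 69% versus 91% observed, that is 55% versus 18% leaving early. With no true effect the means differ by 0.218. At 50 per arm z = 0.71, rejection 11%; at 207 per arm z = 1.44, rejection 30%.

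**Equal follow-up.** λ = 0.4 in both arms (82% observed), 50 per arm, rate ratio 0.5: t-test z = 0.412/0.256 = 1.61, power 0.36; rate comparison z = 0.693/0.404 = 1.71, power 0.40.

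**Simulation, same assumptions** (quasi-Poisson model with offset as comparator):

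| Scenario | t-test | Rate model |
|---|---|---|
| 86% vs 79%, 50/arm, rate ratio 0.5 | 0.29 | 0.42 |
| 86% vs 79%, 207/arm, rate ratio 0.6 | 0.56 | 0.76 |
| 86% vs 79%, no effect, 50/arm | about 5-6% | about 5% |
| 86% vs 79%, no effect, 207/arm | 7-8% | about 6% |
| 91% vs 69%, no effect, 50/arm | about 10% | about 6% |
| 91% vs 69%, no effect, 207/arm | about 30% | 6-7% |
| 82% both arms, 50/arm, rate ratio 0.5 | 0.37 | 0.43 |
| 82% both arms, 207/arm, rate ratio 0.6 | 0.72 | 0.755 |

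**Different assumptions.** I also took 0.02 to 0.1 events per patient-month, all groups pooled, and early stopping of 40% in controls versus 20% in the experimental arm (mean follow-up 4.4 versus 4.9 months). At equal rates the mean-count ratio is about 1.11. Null rejection by t-test is 6.5% to 9.6% for counts and 5.0% to 7.5% for hospital days. Power for a true halving of the event count is 0.40 versus 0.52 at the low rate and 0.88 versus 0.97 at the high rate.

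**The case against.** The strongest reply is that the size of the problem rests on assumed figures. The protocol states no event rates, zeros or dropout, and its expectation that patients will stay on treatment longer is hedged. The 10% and 30% rejection rates need 55% of controls to leave early against 18% of experimental patients, together with no effect on visits. Nothing in the document supports that combination, and the 207-per-arm figure belongs to the adjuvant chemotherapy group. This stands: those figures are an outer bound.

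A reader might also infer that the t-test fails because the counts are full of zeros and skewed. That is not supported. A high share of zeros is plausible but not documented. With equal follow-up the loss is about 4-6 points, and part of that reflects the rate model's slightly higher null rejection.

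Nor is the false-positive problem worst in the small groups: under moderate imbalance the t-test stays near nominal at 50 per arm, and the inflation is larger at 207. The different planned windows are not a source of bias either, since randomisation is within subgroup.

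Finally, the offset has assumptions of its own: a roughly constant rate and exit unrelated to the event rate. Exit for unacceptable toxicity may break the second. If two-thirds of events fell in the first third of the window (assumed), the rate model in the extreme null scenario at 207 per arm would reject 8.2% of the time, 7.4 points of it favouring the nurse arm. This limits the remedy but does not rescue unscaled counts.

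**Conclusion.** The point holds in a limited form. Section 5.3 fixes a t-test for quantitative outcomes, section 2 defines these outcomes as numbers, and section 3.3 makes time observed unequal for reasons the intervention may affect. That the test would be run on unscaled counts is inferred from these definitions; the text offers no other reading.

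If experimental patients stay on study longer, the comparison is biased against the intervention. With 86% versus 79% of the window observed, equal rates look like about 10% more events in the experimental arm. Power falls by about 13 points at 50 per arm (0.42 to 0.29) and 20 points at 207 per arm (0.76 to 0.56). The false-positive rate moves modestly, to about 5-6% and 7-8%. All of this depends on assumed overdispersion, event rates and exit patterns. If exit does not differ by arm, little is lost.

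The affected endpoints are secondary; the primary outcome's sample size is untouched.

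**What to change.** In section 5.3, state that emergency accesses, unplanned visits, admissions and hospital days will be analysed with a negative binomial or quasi-Poisson model, with log(days observed) as offset and treatment subgroup as a factor where groups are combined. Report a rate ratio with 95% CI. At 50 per arm, add a permutation p-value as a check.

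Also state that time on study will be reported by arm, and add a sensitivity analysis by period of follow-up to test the constant-rate assumption.

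The cost is a few sentences of analysis text, with no new patients or visits. One item needs confirming: the protocol does not say that the end-of-observation date is recorded in the eCRF, and the offset needs it. The drawbacks are a slightly inflated error rate in small groups (about 6% in simulation) and reliance on non-informative exit, which the report by arm and the period analysis can expose but not remove.

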- c) in case of toxicities that need an urgent intervention (less than 12 hours): facilitation of the contact with the referral physician or, if the contact is not possible, suggestion to access to the hospital through the centre-specific modalities (access

to the emergency room, access to the supportive care service, and so on);

d) in case of not deferrable urgencies: direct access to the emergency room through the emergency services (118).

At the end of every phone call, the Nurse Operative Center gives a synthetic report of the detection and sends an appropriate email to the reference physicians (identified at the moment of randomisation).

During the evaluation period, according to the PRO-CTCAE (validated in Italian) (53) (Attachment 1, 2, 3), in both groups, a questionnaire for the monitoring of toxicities will be administered to each patient.

This questionnaire, which takes into consideration the previous week, monitors the frequency (F), severity (S), and intensity (I) of each symptom. A question about the number of days spent with toxicity will be performed. The administration of the questionnaire will be made through a pre-registered phone call (without an operator), which is based on an electronic score coding. This phone call does not overlap with the monitoring phone call in the specific randomisation group.

For the patients' privacy, every date coming from the project will be dealt with according to the current laws.

In each group, at the baseline visit, then every month, the EORTC QLQ-C30 questionnaire (Attachment 4) will be administered.

In both groups, there will be a monitoring activity of the number of unplanned hospital accesses (emergency room or specialist visits). An evaluation of the number of hospital admissions and days of hospital stay (due to toxicities) will be performed.

Finally, the dose intensity of the oncological drugs throughout the period of treatment will be monitored (it will be considered as the ratio between the administered dose and the planned dose). This aspect is fundamental not only for the management of the oncological therapy but also for the adherence to the recommendations of supportive care.

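### Protocol section 5.3 tests changes over time with a two-way ANOVA that has no patient term, although QLQ-C30 is repeated monthly on the same patients

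*Protocol*

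**What the plan says.** Section 5.3 of the protocol fixes the method for change over time: "The statistical significance of the variations in time of quantitative variables will be performed through the two-way analysis of variance (ANOVA". It names no factors, no patient effect and no repeated-measures structure. Differences between the arms in quantitative variables go to a separate test, the Student's "t-test for dependent groups in case of quantitative parameters". This is the only mention of dependence in the section, and it is attached to the comparison of two randomised arms.

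The main repeated quantitative outcome is the quality-of-life questionnaire described in section 4: "In each group, at the baseline visit, then every month, the EORTC QLQ-C30 questionnaire (Attachment 4) will be administered". Section 3.3 sets the follow-up: "The study period will be 4 months for the immunotherapy and targeted therapy groups and 6 months for the adjuvant chemotherapy group". It also foresees early exit: "The study can be interrupted earlier in case of oncological treatment discontinuation because of disease progression, unacceptable toxicity, or withdrawal of consent", and it adds death to that list. Section 2 lists "Evaluation of quality of life" among the secondary objectives.

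**The concern.** Scores from one patient at successive months are normally positively correlated. A two-way ANOVA with arm and time as factors and no patient term places the stable differences between patients in the residual. Time and arm × time are within-patient comparisons, so they are then judged against too large an error and reject too rarely. The arm comparison is between patients and is judged against too small an error. A nominal 5% test is then not a 5% test in either direction.

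What is at stake is the reading of a named secondary endpoint. A real difference in how quality of life evolves could be reported as no difference. The risk is greatest in groups B and C, which have 50 patients per arm.

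**Working it through.** **The plan's own figures.** The protocol gives no figure for the ANOVA, so only its sample sizes can be reproduced. The two-sided formula for two proportions is n₀ = [1.96·√(2p̄q̄) + z_power·√(p₁q₁ + p₂q₂)]²/Δ², with continuity correction n = (n₀/4)·[1 + √(1 + 4/(n₀Δ))]².

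- Group A (15% v 5%, power 0.90): n₀ = 187.05, n = 206.6, so 207. This agrees with "it is then necessary to have 207 patients for each arm of the study".
- Groups B and C (25% v 5%, power 0.72): n₀ = 40.5, n = 49.97, so 50. This agrees with "it is then necessary to have 50 patients per" arm.
- Total: 2×207 + 4×50 = 614, as stated.

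These are the arm sizes used below.

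**Inputs.** Scores per patient m: 1 + 4 = 5 in B/C and 1 + 6 = 7 in A (sections 3.3 and 4). Patients per arm n: 50 and 207. Assumed, because the protocol gives none of them: SD 1, complete data, and within-patient correlation ρ of 0.2, 0.3, 0.5 or 0.7, with either compound symmetry or AR(1).

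**Expected mean squares under compound symmetry, no true effect**
- arm: 1 + (m−1)ρ
- time and arm × time: 1 − ρ
- pooled residual: {[1 + (m−1)ρ] + (m−1)(1−ρ)}/m = 1

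The arm × time F ratio is therefore shrunk by 1 − ρ, and the arm F ratio is inflated by 1 + (m−1)ρ.

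**Hand check.** Treating the residual as fixed at 1:
- B/C, ρ = 0.5: the 5% critical F on 4 and 2×49×5 = 490 df is 2.39. Rejection needs χ²₄ > 2.39×4/0.5 = 19.1, probability about 0.07%. Allowing for the varying residual gives 0.1%.
- A, ρ = 0.3: the critical F on 6 and 2×206×7 = 2884 df is 2.10. Rejection needs χ²₆ > 2.10×6/0.7 = 18.0, probability 0.6%.

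**Null rejection of arm × time, ordinary ANOVA, nominal 5%**

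| | ρ = 0.2 | 0.3 | 0.5 | 0.7 |
|---|---|---|---|---|
| B/C, compound symmetry | 1.9% | 0.9% | 0.1% | 0.0% |
| A, compound symmetry | 1.5% | 0.6% | 0.04% | 0.0% |
| B/C, AR(1) | 3.5% | 2.9% | 1.7% | 0.4% |
| A, AR(1) | 4.3% | 3.4% | 2.3% | 1.1% |

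In B/C under compound symmetry the time test behaves alike (2.2%, 1.0%, 0.1%, 0.0%). With the patient as error stratum, the arm × time rate is 4.6% to 5.4% under compound symmetry. Under AR(1) without a sphericity correction it is 5.1% to 6.8% in B/C and 5.7% to 8.5% in A.

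**Power of arm × time, ordinary ANOVA v patient as error stratum (simulated)**

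| Assumed effect | ρ = 0.2 | 0.3 | 0.5 | 0.7 |
|---|---|---|---|---|
| B/C, linear to 0.5 SD, compound symmetry | 0.24 v 0.37 | 0.20 v 0.43 | 0.13 v 0.58 | 0.05 v 0.83 |
| B/C, linear to 0.5 SD, AR(1) | 0.28 v 0.34 | 0.27 v 0.36 | 0.23 v 0.42 | 0.18 v 0.53 |
| B/C, linear to 0.8 SD, compound symmetry | 0.70 v 0.82 | 0.69 v 0.87 | 0.67 v 0.96 | 0.65 v 1.00 |
| A, linear to 0.3 SD, compound symmetry | 0.40 v 0.59 | 0.36 v 0.65 | 0.26 v 0.81 | 0.13 v 0.98 |

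In A at 0.5 SD almost nothing is lost (0.95–0.98 v 0.98–1.00). The AR(1) row slightly flatters the patient-stratum test, which is uncorrected there.

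**Arm term, only if it were interpreted.** The false-positive rate is 2·[1 − Φ(1.96/√(1 + (m−1)ρ))]. For m = 5 this gives 14%, 19%, 26% and 31%; for m = 7, 19%, 24%, 33% and 39%. Under AR(1) in B/C it is about 9% to 26%.

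**The case against.** The strongest reply is that section 5.3 is terse rather than wrong. Factors, error strata and covariance are often left to a statistical analysis plan, which may exist here. Two-way ANOVA for change over time can also mean patient × time, or arm × time with repeated measures. On those readings the patient is in the model and the error rates are near 5%. This stands to a point: the harm quantified above belongs to one of several readings. But the protocol does choose and name a method, nothing in the text points to a patient-aware version, and the patient-aware version in its classical form still loses every patient with a missing month.

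It can also be said that section 5.3 names no arm × time hypothesis and gives arm differences to the t-test. That is correct. The power figures show what would follow if the ANOVA were used to compare the arms' courses, not a loss on a test the protocol has declared.

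A reader might infer that the plan would produce false claims of benefit on quality of life. The documents do not support that. On the ordinary reading the time and arm × time tests err on the conservative side, and the 9% to 39% false-positive rate applies only to an ANOVA arm term that the protocol does not say it will interpret. Nor do they support a reading that the primary endpoint or the 614 patients are affected: the ANOVA sentence does not enter the sample size, and arm differences in quantitative variables are assigned to another test.

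**Conclusion.** The point holds as a badly fixed method for secondary repeated variables, and it should be corrected. The direction is the same at every positive correlation tried. The size rests on assumed correlations, effects and complete data. It ranges from slight (AR(1) at ρ = 0.2, or large effects) to a near-total loss of sensitivity (compound symmetry at ρ = 0.7 with a linear divergence to 0.5 SD in B/C). At ρ = 0.5 in B/C, power for that divergence is 0.13 instead of 0.58 under compound symmetry, and 0.23 instead of 0.42 under AR(1). Part of the difficulty in B and C is simply 50 patients per arm: at ρ = 0.2 even the patient-aware test reaches only 0.34 to 0.37.

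It cannot be concluded that the planned error rates are certainly wrong, because a repeated-measures analysis may have been meant. Either way the sentence needs changing.

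**What to change.** Replace the ANOVA sentence in section 5.3 with:

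> Changes over time in repeated quantitative variables (including QLQ-C30) will be analysed, separately in groups A, B and C, with a linear mixed model for repeated measures with patient as the unit, using all available visits: change from baseline at each month, with arm, month, arm × month and baseline score as fixed effects and unstructured within-patient covariance; mean change per arm and month and the arm difference will be reported with 95% CI.

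Add that, for these variables, the arm difference from this model replaces the separate t-test, so that there is one arm comparison and not two. State in advance whether that difference is the average over months or the one at the last month. The arm × month test should be supportive only: with baseline as a covariate it cannot detect a constant difference after baseline.

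The covariance has 4×5/2 = 10 parameters in B or C (100 patients each) and 6×7/2 = 21 in A (414 patients), which these numbers can support. The cost is a short text change and slightly more analysis work; no data are added, and the primary endpoint and sample size stay as they are. The drawback is a missing-at-random assumption, which should be noted given exits for progression, toxicity or death. If a repeated-measures ANOVA was intended, saying so with a sphericity correction would repair the error rates, but its classical form would still discard patients with a missing month.
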